5.3.5.13 Cases of Accidental Overdose or Medication Error

Accidental overdose and medication error (hereafter collectively referred to as "special situations") are defined as follows:

- Accidental overdose: accidental administration of a drug in a quantity that is higher than the assigned dose
- Medication error: accidental deviation in the administration of a drug

In some cases, a medication error may be intercepted prior to administration of the drug.

Special situations are not in themselves adverse events, but may result in adverse events. Each adverse event associated with a special situation should be recorded separately on the adverse event eCRF. If the associated adverse event fulfills seriousness criteria *or qualifies as an adverse event of special interest*, the event should be reported to the Sponsor immediately (i.e., no more than 24 hours after learning of the event; see Section 5.4.2). For gantenerumab, adverse events associated with special situations should be recorded as described below for each situation:

- Accidental overdose: Enter the adverse event term. Check the "Accidental overdose" and "Medication error" boxes.
- Medication error that does not qualify as an overdose: Enter the adverse event term. Check the "Medication error" box.
- Medication error that qualifies as an overdose: Enter the adverse event term. Check the "Accidental overdose" and "Medication error" boxes.

In addition, all special situations associated with gantenerumab, regardless of whether they result in an adverse event, should be recorded on the adverse event eCRF as described below:

- Accidental overdose: Enter the drug name and "accidental overdose" as the event term. Check the "Accidental overdose" and "Medication error" boxes
- Medication error that does not qualify as an overdose: Enter the name of the drug administered and a description of the error (e.g., wrong dose administered, wrong dosing schedule, incorrect route of administration, wrong drug, expired drug administered) as the event term. Check the "Medication error" box
- Medication error that qualifies as an overdose: Enter the drug name and "Accidental overdose" as the event term. Check the "Accidental overdose" and "Medication error" boxes. Enter a description of the error in the additional case details
- Intercepted medication error: Enter the drug name and "intercepted medication error" as the event term. Check the "Medication error" box. Enter a description of the error in the additional case details.

As an example, an accidental overdose that resulted in a headache would require two entries on the adverse event eCRF, one entry to report the accidental overdose and one

entry to report the headache. The "Accidental overdose" and "Medication error" boxes would need to be checked for both entries.

5.4 IMMEDIATE REPORTING REQUIREMENTS FROM INVESTIGATOR TO SPONSOR

Certain events require immediate reporting to allow the Sponsor to take appropriate measures to address potential new risks in a clinical study. The investigator must report such events to the Sponsor immediately; under no circumstances should reporting take place more than 24 hours after the investigator learns of the event. The following is a list of events that the investigator must report to the Sponsor within 24 hours after learning of the event, regardless of relationship to study drug:

- Serious adverse events (defined in Section 5.2.2; see Section 5.4.2 for details on reporting requirements)
- Adverse events of special interest (defined in Section 5.2.3; see Section 5.4.2 for details on reporting requirements)
- Pregnancies (see Section 5.4.3 for details on reporting requirements)
- Medical device complaints (see Section 5.4.4 for details on reporting requirements)

For serious adverse events and adverse events of special interest, the investigator must report new significant follow-up information to the Sponsor immediately (i.e., no more than 24 hours after becoming aware of the information). New significant information includes the following:

- New signs or symptoms or a change in the diagnosis
- Significant new diagnostic test results
- Change in causality based on new information
- Change in the event's outcome, including recovery
- Additional narrative information on the clinical course of the event

Investigators must also comply with local requirements for reporting serious adverse events to the local health authority and IRB/EC.

5.4.2 Reporting Requirements for Serious Adverse Events and Adverse Events of Special Interest

5.4.2.1 Events That Occur prior to Study Drug Initiation

After informed consent has been obtained but prior to initiation of study drug, only serious adverse events caused by a protocol-mandated intervention should be reported.

The paper Clinical Trial Adverse Event/Special Situations Form provided to investigators should be completed and submitted to the Sponsor or its designee immediately (i.e., no more than 24 hours after learning of the event), either by faxing or by scanning and emailing the form using the fax number or email address provided to investigators.

5.4.2.2 Events That Occur after Study Drug Initiation

After initiation of study drug, serious adverse events and adverse events of special interest will be reported until the participant's last visit (including long-term follow-up visits). Investigators should record all case details that can be gathered immediately (i.e., within 24 hours after learning of the event) on the adverse event eCRF and submit the report via the electronic data capture (EDC) system. A report will be generated and sent to Roche Safety Risk Management by the EDC system.

In the event that the EDC system is unavailable, the paper *Clinical Trial Adverse Event/Special Situations* Form provided to investigators should be completed and submitted to the Sponsor or its designee immediately (i.e., no more than 24 hours after learning of the event), either by faxing or by scanning and emailing the form using the fax number or email address provided to investigators. Once the EDC system is available, all information will need to be entered and submitted via the EDC system.

Instructions for reporting serious adverse events that occur after the adverse event reporting period are provided in Section 5.6.

5.4.3 Reporting Requirements for Pregnancies

5.4.3.1 Pregnancies in Female Participants

Female participants of childbearing potential will be instructed *through the Informed Consent Form* to immediately inform the investigator if they become pregnant during the study or within 16 weeks after the last dose of study drug. A paper Clinical Trial Pregnancy Reporting Form should be completed and submitted to the Sponsor or its designee immediately (i.e., no more than 24 hours after learning of the pregnancy),

either by faxing or by scanning and emailing the form using the fax number or email address provided to investigators. Pregnancy should not be recorded on the adverse event eCRF. The investigator should discontinue study drug and counsel the participant, discussing the risks of the pregnancy and the possible effects on the fetus. Monitoring of the participant should continue until conclusion of the pregnancy. Any serious adverse event associated with the pregnancy (e.g., an event in the fetus, an event in the mother during or after the pregnancy, or a congenital anomaly/birth defect in the child) should be reported on the adverse event eCRF. In addition, the investigator will submit a Clinical Trial Pregnancy Reporting Form when updated information on the course and outcome of the pregnancy becomes available.

5.4.3.2 Abortions

A spontaneous abortion should be classified as a serious adverse event (as the Sponsor considers abortions to be medically significant), recorded on the adverse event eCRF, and reported to the Sponsor immediately (i.e., no more than 24 hours after learning of the event; see Section 5.4.2).

If a therapeutic or elective abortion was performed because of an underlying maternal or embryo-fetal toxicity, the toxicity should be classified as a serious adverse event, recorded on the adverse event eCRF, and reported to the Sponsor immediately (i.e., no more than 24 hours after learning of the event; see Section 5.4.2). A therapeutic or elective abortion performed for reasons other than an underlying maternal or embryo-fetal toxicity is not considered an adverse event.

All abortions should be reported as pregnancy outcomes on the paper Clinical Trial Pregnancy Reporting Form.

5.4.3.3 Congenital Anomalies/Birth Defects

Any congenital anomaly/birth defect in a child born to a female participant exposed to study drug should be classified as a serious adverse event, recorded on the adverse event eCRF, and reported to the Sponsor immediately (i.e., no more than 24 hours after learning of the event; see Section 5.4.2).

5.4.4 Reporting Requirements for Medical Device Complaints

The investigator must report all medical device complaints (e.g., devices for study drug administration) to the Sponsor. The investigator should document as much information as possible on the IMP Deviation Form, including the product batch number, and forward the form to the Sponsor immediately (i.e., no more than 24 hours after learning of the event) (refer to the pharmacy manual for further details). If the medical device results in an adverse event to the study participant, the event must be reported on the adverse event eCRF and submitted through the EDC system. If the event is serious, the adverse event eCRF must be completed immediately (i.e., no more than 24 hours after learning of the event), as outlined in Section 5.4.2.

5.5 FOLLOW-UP OF *PARTICIPANTS* AFTER ADVERSE EVENTS

5.5.1 Investigator Follow-Up

The investigator should follow each adverse event until the event has resolved to baseline grade or better, the event is assessed as stable by the investigator, the participant is lost to follow-up, or the participant withdraws consent. Every effort should be made to follow all serious adverse events considered to be related to study drug or study-related procedures until a final outcome can be reported.

During the study period, resolution of adverse events (with dates) should be documented on the adverse event eCRF and in the participant's medical record to facilitate source data verification.

All pregnancies reported during the study should be followed until pregnancy outcome.

5.5.2 Sponsor Follow-Up

For serious adverse events, adverse events of special interest, and pregnancies, the Sponsor or a designee may follow up by telephone, fax, email, and/or a monitoring visit to obtain additional case details and outcome information (e.g., from hospital discharge summaries, consultant reports, autopsy reports) to perform an independent medical assessment of the reported case.

5.6 ADVERSE EVENTS THAT OCCUR AFTER THE ADVERSE EVENT REPORTING PERIOD

The Sponsor should be notified if the investigator becomes aware of any serious adverse event that occurs after the end of the adverse event reporting period (defined as the participant's last study visit), if the event is believed to be related to prior study drug treatment. These events should be reported through use of the adverse event eCRF. However, if the EDC system is not available, the investigator should report these events directly to the Sponsor or its designee, either by faxing or by scanning and emailing the paper Clinical Trial Adverse Event/Special *Situations* Form using the fax number or email address provided to investigators.

5.7 EXPEDITED REPORTING TO HEALTH AUTHORITIES, INVESTIGATORS, INSTITUTIONAL REVIEW BOARDS, AND ETHICS COMMITTEES

The Sponsor will promptly evaluate all serious adverse events and adverse events of special interest against cumulative product experience to identify and expeditiously communicate possible new safety findings to investigators, IRBs, ECs, and applicable health authorities based on applicable legislation.

To determine reporting requirements for single adverse event cases, the Sponsor will assess the expectedness of these events through use of the reference safety information in the document listed below:

Drug	Document
Gantenerumab	Gantenerumab Investigator's Brochure

The Sponsor will compare the severity of each event and the cumulative event frequency reported for the study with the severity and frequency reported in the applicable reference document.

Reporting requirements will also be based on the investigator's assessment of causality and seriousness, with allowance for upgrading by the Sponsor as needed.

6. STATISTICAL CONSIDERATIONS AND ANALYSIS PLAN

6.1 DETERMINATION OF SAMPLE SIZE

The purpose of this study is to assess the long-term safety and tolerability of gantenerumab in participants who complete the OLEs of Studies WN25203 or WN28745. The sample size will include all eligible participants who consent to this study.

Therefore, *in Part 1 of the study*, the sample size *was* driven by the number of participants who complete the OLE part of Studies WN25203 or WN28745 and subsequently enrolled in this study. *There were 116 participants that participated in Part 1 of the study.*

For Part 2, the sample size is expected to be no more than 116 participants.

6.2 SUMMARIES OF CONDUCT OF STUDY

Participant disposition (including withdrawals from treatment) and protocol deviations will be summarized descriptively for all participants in the safety population who receive at least one dose of treatment in this study.

6.3 SUMMARIES OF DEMOGRAPHIC AND BASELINE CHARACTERISTICS

Demographic and baseline characteristics (such as age, sex, race, disease stage, and APOE ε4 status) will be summarized descriptively for all participants enrolled in the safety population.

Descriptive summaries of continuous data will present the mean, SD, median, and minimum and maximum. Descriptive summaries of discrete data will include frequencies expressed in terms of the number and percentage of participants.

6.4 EFFICACY ANALYSES

There will be no formal confirmatory efficacy analyses for this study.

6.4.1 Exploratory Efficacy Endpoints

To monitor AD progression, MMSE will be summarized using mean, SD, median, inter-quartile range and minimum and maximum. No hypothesis testing will be performed.

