Participants will be treated for 2 years, followed by a safety and MMSE assessment 4 weeks following the last dose (follow-up visit; see Schedule of Activities).

Participants who discontinue study drug at any time during this study will be asked to complete an early termination visit 4 weeks after their last dose (early termination visit; see [Appendix 1](#)).

3.1.2 Overview of the Study Design in Part 2

All participants who are actively enrolled in Part 1 of Study WN41874 (i.e., have completed Week 104 visit in Part 1 and have not discontinued from study drug per Section 4.6.1) will be invited to participate in Part 2 of the study.

Informed consent should be obtained by participants while they are active in the Part 1 of the study.

In Part 2 of the study, participants who have previously completed the Week 104 visit, (i.e., without having to perform a follow up visit post Week 104 in Part 1) can continue receiving open-label gantenerumab for additional 2 years. Additionally, participants might also have an option of participating in another open label extension study while completing the Part 2 of the study.

Gantenerumab will be administered by SC injection Q4W at the same dose as administered in the Part 1 of the study. There is a ± 7 day window for all visits. However, the minimal time between doses is 21 days, and the target day for each Q4W visit is timed with respect to baseline, not to the prior visit.

Participants will be treated for an additional 2 years, followed by a safety and MMSE assessment 4 weeks following the last dose (follow-up visit; see [Appendix 1](#)).
Participants will undergo tests of safety, efficacy as per the schedule of assessments.

The end of the study will be considered as the follow-up visit 4 weeks after the last dose for the last participant that enrolled over to Part 2.

All participants have the right to voluntarily discontinue study drug or withdraw from the study at any time for any reason.

Participants who discontinue study drug at any time during this study will be asked to complete a follow-up visit at 4 weeks after their last dose (*early termination visit*; see [Appendix 1](#)).

Participants who do not want to participate in Part 2 of the study will be discontinued from the study and will be asked to complete follow up visit 4 weeks after the last dose as per the Schedule of Assessments (follow up visit; see [Appendix 1](#)).

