4.1.2 Exclusion Criteria

Participants who met any of the following criteria *will* not be eligible:

- Prematurely discontinued from the OLEs of Studies WN25203 or WN28745 or from study drug for any reason
- Any medical condition that the investigator or Sponsor determines may jeopardize the participant’s safety if he or she continues to receive study treatment
- If the participant is unlikely to benefit from gantenerumab therapy, based on disease progression or other factors, or if study participation is otherwise not in the participant’s best interest, by determination of the investigator or Sponsor
- Any investigational treatment other than gantenerumab during or since completion of the OLEs of Studies WN25203 or WN28745
- Pregnancy
- Evidence of disseminated leptomeningeal hemosiderosis (i.e., more than three focal leptomeningeal hemosiderosis)
- Evidence of intracerebral macrohemorrhage

4.1.3 Eligibility in Part 2

- *All participants who have completed Week 104 visit in Part 1 of the study and have not been discontinued from Part 1 of the study can continue to participate in Part 2 of the study*
- *The criteria mentioned in Sections 4.1.1 and 4.1.2 will also be applicable to Part 2 of the study*

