6.5 SAFETY ANALYSES

The safety analysis population will include all participants in the safety population who received at least one dose of study drug. The following safety outcome measures will be summarized using descriptive statistics:

- Incidence, nature, severity, and timing of adverse events
- Incidence, nature, severity, and timing of serious adverse events
- Changes from baseline of this study in vital signs, blood tests, ECGs, and C-SSRS
- Incidence, nature, severity, and timing of MRI safety findings: ARIA-E and ARIA-H
- Incidence, nature, severity, and timing of ISRs
- Number and proportion of ADA-positive and ADA-negative participants during both the treatment and follow-up periods
- Incidence of treatment discontinuations for adverse events
- Incidence of adverse events of special interest

Statistical methods, endpoint definitions and analyses of the safety endpoints will be described in the Statistical Analysis Plan.

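### The MMSE plan names no within-person change score, so visit means over 4 years could mix progression with a change in who is measured, notably at Week 104

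*Combined protocol and SAP*

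**What the plan says.** Section 6.4.1, repeated in the synopsis, states: "To monitor AD progression, MMSE will be summarized using mean, SD, median, inter-quartile range and minimum and maximum". No hypothesis test is planned, and Section 6.4 rules out confirmatory efficacy analysis. Table 1 in Section 2 makes MMSE total score the one endpoint under the exploratory efficacy objective, for assessing progression.

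Section 6.5 does ask for change scores elsewhere: "Changes from baseline of this study in vital signs, blood tests, ECGs, and C-SSRS". Its reference to a further document covers safety only: "Statistical methods, endpoint definitions and analyses of the safety endpoints will be described in the Statistical Analysis Plan".

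Four provisions bear on who is measured after Week 104:

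- Section 3.1.2: completers of Week 104 who are still on drug "will be invited to participate in Part 2 of the study".
- Section 3.1.2: "Participants who do not want to participate in Part 2 of the study will be discontinued from the study".
- Section 3.1.2: "participants might also have an option of participating in another open label extension study while completing the Part 2 of the study".
- Section 4.1.3: "The criteria mentioned in Sections 4.1.1 and 4.1.2 will also be applicable to Part 2 of the study". One of those criteria, in Section 4.1.2, reads "If the participant is unlikely to benefit from gantenerumab therapy, based on disease progression or other factors". It is decided by the investigator or Sponsor, with no MMSE cut-off.

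People who leave are asked for one visit 4 weeks after the last dose (Sections 3.1.2 and 4.6.2). Appendix 1 schedules MMSE at Day 1, Weeks 24, 52, 76, 104, 128, 156, 180 and 208, and at follow-up.

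**The concern.** Progression is change within a person. A mean at each visit shows it cleanly only if the same people, or an unselected subset of them, are present at each visit. Here the composition can shift at any visit and has an obvious chance to shift at Week 104. If those who leave score lower than those who stay, later means are lifted and decline looks slower. If those who leave score higher, decline looks faster.

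There is no control arm in which the same shift would show, so a change in case mix at Week 128 could be read as a change in the rate of decline. Section 6.2 summarizes disposition, but no stated analysis links it to MMSE. What is at stake is how one exploratory result is interpreted. The safety objective is not affected.

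**Working it through.** The plan gives no figure to reproduce: there is no power statement, and N = 116 is simply the number in Part 1. It also gives no MMSE mean, SD, slope, exit rate or Part 2 uptake, so **every input below is an assumption**.

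**1. The Week 104 step in closed form.** Suppose a fraction q does not enter Part 2, and the tendency to enter has correlation rho with Week 104 MMSE. With normal scores, the mean of those who stay exceeds the mean of all by

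shift = rho × SD × phi(z_q) / (1 - q).

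With SD 6, q = 0.20 and rho = 0.5: 0.5 × 6 × 0.280 / 0.80 = 1.05 points. A true 24-week decline of 1.5 would then appear as about -1.5 + 1.05 = -0.45 in visit means (-0.46 by simulation), while the paired change in those who stay is -1.49. For SD 4 to 8, q 0.1 to 0.3 and rho 0.3 to 0.8, the shift is 0.23 to 3.18 points, the difference in visit means runs from -1.28 to +1.64, and the paired change stays between -1.49 and -1.51. With rho = 0 the shift is 0. A negative rho reverses its sign.

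**2. Four-year simulation.** Person-level intercept 19 (SD 5), slope -2.5 per year (SD 1.8), error SD 1.8, scores rounded and held within 0 to 30, at the nine scheduled visits. Exit probability in an interval is 1 - exp(-hazard × years). The linear trend gives -2.5 × 4 = -10; the floor at 0 brings the full-cohort change to about -9.25.

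| Assumed pattern of leaving | Difference in visit means, Day 1 to Week 208 | Against -9.25 |
|---|---|---|
| Unrelated to MMSE (hazard 0.10, uptake 0.75) | -9.25 | no bias |
| Fitter people leave (hazard 0.05; uptake 0.7 if Week 104 MMSE is 20 or more, else 0.9) | -9.7 | overstated 5% |
| The same, plus 20% exclusion below MMSE 12 | -9.2 | under 1% |
| Exclusion of 10%, 20%, 30% below MMSE 12 (hazard 0.05, uptake 0.9) | -9.0, -8.7, -8.4 | understated 3%, 6%, 9% |
| Exclusion of 60% below MMSE 12 (hazard 0.05, uptake 0.8) | -7.4 | understated 20% |
| Exit linked to low MMSE at every visit, mild; moderate | -8.3; -6.9 | understated 10%; 25% |
| Both: mild with 30% exclusion; moderate with 60% | -7.5; -5.5 | understated 19%; 41% |

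The mild hazard is 0.05 + 0.04 × (18 - MMSE)/6 with uptake 0.9. The moderate hazard is 0.05 + 0.12 × (18 - MMSE)/6 with uptake 0.8. Each percentage is the distance from -9.25 divided by 9.25; for example (9.25 - 5.5)/9.25 = 41%.

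**3. What the added summaries would show in the same runs.**

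- The paired Week 104 to Week 128 change among entrants is about -1.1 in every pattern.
- Change from Day 1 in those still present at Week 208 is closer to -9.25 than the difference in means, but not free of selection: -8.9 with 30% exclusion, -8.5 with 60%, and -7.6 in the strongest combined case.
- Week 104 MMSE in entrants minus non-entrants is about 0 when exit is unrelated, 3.7 to 4.7 with 30% to 60% exclusion, and 0.9 to 1.2 when only visit-by-visit exit is linked to MMSE. With 116 participants this difference has an SD across trials of 1.2 to 1.9. The comparison would therefore reveal selective entry at Week 104, but gradual selective exit only weakly.

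**The case against.** The strongest reply is that the plan may already be adequate. Section 6.4.1 lists statistics. It does not say that they apply to raw scores only, and its stated purpose of following progression implies comparison over time. A reader might infer that change scores are ruled out. The documents do not support that: Section 6.5 refers to a Statistical Analysis Plan, and although that sentence covers only safety endpoints, it does not show that the plan is silent on MMSE. What stands is that the available text commits to no change score for MMSE while it does so for other measures.

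A reader might also infer that Part 2 entry is a progression filter that makes decline look too slow. That goes too far. The criterion also covers other factors, is a judgment, and is the Part 1 criterion carried forward. Completers are invited as a rule, and Sections 4.6.1 and 4.6.2 allow discontinuation in the participant's best interest at any time, so such exits need not cluster at Week 104. Fitter people may leave instead, and opposite tendencies can nearly cancel, as the third row of the table shows.

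Finally, one can produce a mean that rises from Week 104 to Week 128 in 86% of simulated trials, but only by assuming that 60% of those below MMSE 12 are excluded, which is no rule of this protocol. With 10% excluded the figure is about 1%. The large numbers should not be read as forecasts.

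**Conclusion.** The point holds as a minor one. The stated MMSE analysis names no within-person change, and the composition of the group can change over 4 years, with Week 104 the clearest place. Under the assumed inputs the difference in visit means lies between about -9.7 and -5.5 against -9.25. The sign and size in this trial cannot be known from the documents, and zero bias is among the possibilities. The result that does not depend on the pattern of leaving is that the paired Week 104 to Week 128 step recovers the decline in Part 2 entrants.

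The consequence is limited to interpretation. MMSE is exploratory and untested, Section 3.3.3 makes safety the primary objective, and no pattern examined turned the 4-year decline into stability or improvement.

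**What to change.** In Section 6.4.1 keep the existing summaries and add:

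- (a) change in MMSE from Day 1 by visit, with N at each visit, and the paired Week 104 to Week 128 change among Part 2 entrants;
- (b) Week 104 MMSE for those who enter Part 2 and for those who do not.

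A mixed model is not needed. In the same simulations a random intercept and slope model overstated decline by 0.3 to 0.5 points, including 0.31 when exit was unrelated to MMSE and visit means were unbiased. A split by reason for leaving is also best left out, since at most 116 people would yield very small cells.

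The cost is a few lines of text and slight programming on data already scheduled. Two limits should be stated with the results. Change from Day 1 among those remaining is still partly affected by selection (about -8.9 to -7.6 in the cases in step 3, where exit is linked to worse MMSE). The paired step describes Part 2 entrants only. The Day 1 value may also be up to 6 months old (Section 4.5.5), which blurs change from baseline slightly.
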